## 11. MEASUREMENT OF EFFECT

Although the clinical benefit of oral triapine in combination with chemoradiation therapy has not yet been established, the intent of offering this treatment is to provide a possible therapeutic benefit, and thus the patient will be carefully monitored for tumor response and symptom relief in addition to safety and tolerability. Patients will be assessed by standard criteria. For the purposes of this study, patients will undergo a clinical assessment every week while receiving chemotherapy and radiation therapy and at 1 month and 3 months post-treatment. Tumor response will be re-evaluated at the 3-month post-treatment  $^{18}\text{F}$ -FDG PET/CT scan (approximately 150 days +/- 7 days following completion of all treatment).

### 11.1 Antitumor Effect – Solid Tumors

Response and progression will be evaluated in this study using the new international criteria proposed by the revised Response Evaluation Criteria in Solid Tumors (RECIST) guideline (version 1.1) [Eur J Ca 45:228-247, 2009]. Changes in the largest diameter (unidimensional measurement) of the tumor lesions and the shortest diameter in the case of malignant lymph nodes are used in the RECIST criteria.

#### 11.1.1 Definitions

Evaluable for toxicity. All patients will be evaluable for toxicity from the time of their first treatment with triapine and cisplatin.

Evaluable for objective response. Only those patients, have received at least 3 cycles of therapy (cisplatin + triapine), and have had their disease re-evaluated (with a 3 month post treatment PET-CT) will be considered evaluable for response. These patients will have their response classified according to the definitions stated below. (Note: Patients who exhibit objective disease progression prior to the end of cycle 1 will also be considered evaluable.)

Evaluable Non-Target Disease Response. Patients who have lesions present at baseline that are evaluable but do not meet the definitions of measurable disease, have received at least one cycle of therapy, and have had their disease re-evaluated will be considered evaluable for non-target disease. The response assessment is based on the presence, absence, or unequivocal progression of the lesions.

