#### 11.1.4.3 Evaluation of 18F-FDG PET CT Target:

**Complete Response (CR):** A metabolic complete response on PET/CT will be defined as greater than -66% reduction in tumor FDG uptake at sites of abnormal tumor FDG uptake noted on pre-treatment FDG-PET study (considering normal cardiac or liver blood pool).

**Partial Response (PR):** A metabolic partial response on PET/CT will be defined as -25% to -66% reduction in tumor FDG uptake at sites of abnormal tumor FDG uptake noted on pre-treatment FDG-PET study (considering normal cardiac or liver blood pool).

**Progressive Disease (PD):** Progressive metabolic disease on PET/CT is classified as an increase in tumor FDG uptake greater than +25% within the tumor region defined on baseline scan (considering normal cardiac or liver blood pool), or appearance of new FDG uptake in new metastatic lesions.

**Stable Disease (SD):** Stable metabolic response will be defined as a change in tumor FDG uptake by less than +25% (increase) or by less than -25% (decrease) at sites of abnormal tumor FDG uptake (considering normal cardiac or liver blood pool) when compared to pre-treatment FDG-PET study.

Patients with a global deterioration of health status requiring discontinuation of treatment or die without objective evidence of disease progression at that time should be reported to be off study treatment due to "symptomatic deterioration." Every effort should be made to document the objective progression even after discontinuation of treatment.

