## 13. STATISTICAL CONSIDERATIONS

### 13.1 Study Design/Endpoints

The **primary safety endpoint** of this study is DLT, and the first primary objective is the determination of the MTD and recommended phase II dose for oral triapine when used concomitantly with cisplatin chemoradiation.

The **primary PK endpoint** of this study is oral bioavailability of triapine, which will be determined with sufficient precision that the 95% CI of the mean population bioavailability falls within 80-125% of that mean. Based on reported preliminary data and assuming a normal distribution at log base 10 level, a true bioavailability rate of 0.67, and a standard deviation of 0.175 at log base 10 level, with 28 patients on RP2D, we will be able to establish the bioavailability with the 95% confidence interval of the population mean falling within 0.53-0.83.

Other PK parameter, including AUC, Cmax, Tmax and T1/2 will be evaluated in the expansion cohort. Descriptive statistics will be used.

The **secondary efficacy endpoints** include metabolic complete response (mCR) by FDG-PET/CT, clinical overall response (OR), overall survival (OS) and progression free survival (PFS).

For the first dose level, 3 patients were enrolled without issues. Given the scarcity of patients and the thus far favorable toxicity profile, dose level 2 will be enrolled per an accelerated titration approach using a single patient cohort. Dose escalation will revert to the standard 3+3 design if the

patient on dose level 2 experiences a DLT or a  $\geq$  grade 2 toxicity or when dose level 3 is reached. The standard 3+3 design is as follows: Escalation at 0/3 DLTs, dose-reduction if  $>1/3$  DLT, and expansion to 6 if 1/3 DLTs. DLT is defined as the severe toxicity event that leads to the termination of the treatment as defined in section 5.5. The highest dose level where  $<2/6$  DLTs are observed will be declared MTD.

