13.1.1 The RP2D will be determined as described in section 5.1.2. Once the RP2D is determined, two expansion cohorts will be enrolled. Subjects will be enrolled into a non-HIV+ cohort (n=12) to further expand pharmacokinetic investigations and provide additional safety information. Additionally, up to 28 HIV+ cervical cancer patients (including the patients who were treated at the RP2D during the dose escalation stage) will be treated on RP2D to determine whether active HIV antiretroviral therapy impacts the antitumor activity of triapine. A Bayesian continuous monitoring will be used to ensure that the true DLT rate is controlled at 20%. To establish the stopping rule, a week prior distribution of DLT rate is set to be beta ( $\alpha=1, \beta=5$ ). If the posterior probability that the true underlying DLT rate exceeds 20% at RP2D is 70% or higher then the study accrual will be suspended and the toxicity data will be examined by the PI and the research team, who will subsequently decide on whether the trial should be terminated or not.

The enrollment suspension rule using the Bayesian analysis mentioned above can be represented as a table of possible outcomes for DLTs, as shown below.

Bayesian rule for suspending enrollment	
Suspend accrual if n patients experience a DLT	in N patients treated
2	3-4
3	5-8
4	9-13
5	14-17
6	18-22
7	23-26
8	27

The operating characteristics of this study design can be expressed in terms of probability of early suspending the enrollment at RD2P under the assumptions of various the true rates of DLT. The following table calculated these probabilities for a single dose level based on the simulation of 10,000 hypothetical trials.

Frequentist properties of Bayesian rule for suspending enrollment		
Probability of DLT	Probability of suspending	Median sample size for

	the enrollment	each dose level
0.1	0.10	28
0.17	0.32	28
0.2	0.45	28
0.25	0.66	13
0.3	0.83	8

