### 13.2 Sample Size/Accrual Rate

13.2.1 The number patients accrued to the study will depend on the MTD; an additional 12 cervical cancer patients may be treated at the RP2D to further define the spectrum of toxicities associated with the regimen and up to an additional 28 HIV+ patients will be enrolled to explore whether active (HIV) antiretroviral therapy impacts the antitumor activity of triapine. Although unlikely to happen, for the worst-case scenario, we could have needed  $6 \times 6 = 36$  patients for the phase dose escalation portion of the protocol, 12 for the non-HIV+ expansion cohort and none of the 6 patients on the MTD (or RP2D) is HIV+ cervical cancer patient. Thus, the maximum number of patients for this trial is  $36 + 12 + 28 = 76$ . Patients who do not complete at least 80% the first cycle of therapy and do not suffer a DLT which leads to the termination of the treatment during the observation period (5 weeks excluding treatment delay period) will not be evaluable and will be replaced. Review of patient toxicity and DLT monitoring will be conducted on a weekly basis by the PI and Phase I clinical team.

We expect that the accrual rate will be approximately 1 per 5 weeks. The follow-up period of the primary endpoint, DLT, is approximately 5 weeks after the starting of the treatment (excluding the treatment delay time as described in section 5.5). During the 3+3 dose escalation stage, we will allow the first 2 patients to be enrolled without stopping. During the expansion cohort, the patients will be accrued continuously. On the other hand, the treatment may be delayed during the DLT follow up period as described in section 5.5. Therefore, for a portion of the patients, the overall follow up time may be longer than 5 weeks. Thus, the accrual rate of 1 per 5 weeks is an estimate considering the facts stated above.

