### 13.3 Data Analysis

#### 13.3.1 Analysis Sets

Evaluable patients: patients who meet all of the protocol inclusion/exclusion criteria and begin treatment with the protocol regimen.

Evaluable patients for DLT: evaluable patients who received at least 80% of the treatment intended during the DLT follow up period as defined in section 5.5 and patients who received any amount of treatment and experienced a protocol defined DLT which leads to the termination of the treatment are evaluable for DLT.

Safety set: data from all evaluable patients who receive initial treatment of the study treatment will be used in the analysis of safety.

Efficacy set: data from all evaluable patients who receive initial treatment of the study treatment will be used in the analysis of efficacy endpoints.

PK and correlative biomarker set: the data from all study-eligible patients (i.e. those meeting all of the protocol inclusion/exclusion criteria) who begin the study treatment and have adequate blood and tissue samples taken will be used in the analyses to address the PK and correlative biomarker aims.

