### 13.3.4 Analysis of Efficacy Endpoints

We will determine the post-therapy, 3-month  $^{18}\text{F}$ -FDG-PET/CT metabolic complete response rate of oral triapine in combination with cisplatin chemoradiation. The mCR rate and the ORR at RP2D will be calculated with corresponding 95% exact confidence interval (CI). The IV triapine version of this regimen has demonstrated a high response rate of  $>90\%$  in patients with stage IB2, II, IIIA, IIIB, and IVA cervical carcinoma. Thus, we could consider the oral treatment not worthy of further study if the response rate is  $<70\%$ . Assuming an inferior margin of 5%, we will conclude that the mCR rate for the study regimen is non-inferior to 70% in this population if we observe at least 23 mCR events in the 28 patients. This is based on a non-inferiority test with type I error of 5%. OS and PFS will be analyzed using the Kaplan-Meier's method. Median survival time will be reported with corresponding 95% CIs.

The proportion of patients experiencing mCR and experiencing objective response will be estimated in both the HIV+ and non-HIV+ cohorts, along with exact 95% binomial confidence intervals. This is an exploratory objective and the trial is not powered for formal statistical tests comparing the cohorts.

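### Section 11.1.1 restricts who is evaluable for response, 13.3.1 puts every eligible treated patient in the efficacy set, and no rule scores a missing 3-month PET, so the reported mCR and ORR can be too high.

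*Combined protocol and SAP*

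**What the plan says.** Section 11.1.1 of the combined protocol and SAP limits evaluability for objective response to "Only those patients, have received at least 3 cycles of therapy (cisplatin + triapine), and have had their disease re-evaluated" with the 3-month post-treatment PET-CT. A note adds patients with objective progression before the end of cycle 1. A separate non-target route needs one cycle and a re-evaluation. Section 5.3.1 speaks of weekly cisplatin cycles, so three cycles is about three weeks; 11.1.1 does not define the term.

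Section 11.1.1 says that evaluable patients are classified by the definitions that follow it. These include 11.1.4.3: "A metabolic complete response on PET/CT will be defined as greater than -66% reduction in tumor FDG uptake".

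Section 13.3.1 defines evaluable differently: the patient is eligible and began treatment. For the efficacy set, "data from all evaluable patients who receive initial treatment of the study treatment will be used in the analysis of efficacy endpoints". Section 13.1 lists the secondary efficacy endpoints, which "include metabolic complete response (mCR) by FDG-PET/CT, clinical overall response (OR), overall survival (OS) and progression free survival (PFS").

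Section 13.3.4 reports mCR and ORR at the RP2D with exact 95% intervals. It concludes non-inferiority to 70%, with a 5-point margin, "if we observe at least 23 mCR events in the 28 patients". It names neither set.

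**The concern.** The word evaluable has two meanings for the same endpoints. Under 13.3.1 the denominator is fixed when treatment starts. Under 11.1.1 it depends on what happens afterwards. A patient who stops before three cycles, dies, withdraws, or progresses after cycle 1 without having the PET can drop out of it.

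No section scores these patients. Sections 9.2.1.5 and 11.1.4.3 make deterioration or death without documented progression a reason for being off treatment and assign no response category.

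Such exclusions are plausible. Section 6.3 takes patients with grade 4 neutropenia off protocol therapy, and the escalation table in 5.1.3 shows grade 4 neutrophil decrease in 2 of 10 patients, without dose level or timing. The IV-triapine mCR in 2.2.1, 23 of 24 (96%), also counts only patients who were imaged.

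At stake are the reported mCR, ORR and their intervals, which are read against the plan's 70% benchmark.

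**Working it through.** **Inputs.** From 13.3.4: n = 28, count 23, reference 70%, margin 5 points (null rate 0.70 − 0.05 = 0.65), type I error 5%. Assumed, because the documents give no figure: the number excluded, k = 2, 3 or 4 of 28, and the mCR rate among them, r = 0, 0.5 or 0.65.

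**1. The plan's own rule.** Exact binomial: P(X ≥ 23 | 28, 0.65) = 0.0393 and P(X ≥ 22 | 28, 0.65) = 0.0923. So 23 is the smallest count that passes at one-sided 5%. The rule reproduces, for a fixed denominator of 28.

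**2. Same events, smaller denominator.** Take 21 mCR and no mCR among the excluded (upper bound), with exact (Clopper–Pearson) intervals:

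| Excluded | mCR / n | Rate | 95% CI |
|---|---|---|---|
| 0 | 21/28 | 75.0% | 55.1–89.3% |
| 2 | 21/26 | 80.8% | 60.6–93.4% |
| 3 | 21/25 | 84.0% | 63.9–95.5% |
| 4 | 21/24 | 87.5% | 67.6–97.3% |

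**3. Expected shift.** With a true all-treated rate of 65%, the rate among retained patients is q = (28 × 0.65 − k × r) / (28 − k), where 28 × 0.65 = 18.2.

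| k | r = 0 | r = 0.5 | r = 0.65 |
|---|---|---|---|
| 2 | 18.2/26 = 70.0% | 17.2/26 = 66.2% | 65.0% |
| 3 | 18.2/25 = 72.8% | 16.7/25 = 66.8% | 65.0% |
| 4 | 18.2/24 = 75.8% | 16.2/24 = 67.5% | 65.0% |

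**4. The decision.** With the count held at 23 and no replacement, excluding a patient cannot add an mCR. If the excluded have none, the count is unchanged and the type I error at 65% stays at 3.9%. The 21 mCR of step 2 fail the rule under either denominator. If the test were instead re-run on the evaluable number, 22/28 fails (p = 0.092) while 22/26 passes (p = 0.024).

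**The case against.** The best answer is that section 13 settles the matter. Section 13.3.1 assigns an efficacy set, and nothing in section 13 imports 11.1.1. The 11.1.1 restriction is labelled for objective response and sits under RECIST, while 9.2.1.5 defines mCR with no evaluability condition. On a natural reading of 13.3.4, a patient without a PET simply contributes no mCR event.

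Much of this stands. The reach of 11.1.1 to mCR is an inference, and an analyst working only from section 13 would probably use all eligible treated patients. But 11.1.1 makes the 3-month PET-CT a condition and points to definitions that include metabolic response. Section 13.3.4 does not say which meaning of evaluable applies, and no sentence scores the missing PET. For ORR the restriction applies directly.

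It is also fair that 11.1.1 is not absolute: the non-target route and the cycle 1 progression note keep some patients in. Neither covers a patient with measurable disease who later dies, withdraws or misses the PET.

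Finally, mCR and ORR are secondary, and the shift may be small. If half of the excluded have mCR, it is 1.2 to 2.5 points, against an interval about 34 points wide at 21/28 (89.3 − 55.1 = 34.2). That limits the weight of the point but does not remove the conflict.

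**Conclusion.** The two sections conflict, and the missing-PET rule is absent. Following 11.1.1 selects on events after treatment start and raises the reported mCR and ORR if the excluded respond less often. At a true 65% with 2 to 4 of 28 excluded, the retained rate lies between 65% (excluded respond alike) and 75.8% (four excluded, none with mCR). The number excluded and their response rate are assumptions, so the bias is possible, not established.

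A reader might infer two stronger things.

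- That the non-inferiority test loses its error control. The documents do not support this for the rule as written: 23 in a fixed 28 keeps 3.9%. Control would be at risk only if the cutoff were re-derived on the evaluable number or patients without a PET were replaced, and the plan provides for neither.
- That 23 would be applied to everyone treated at the RP2D. Section 13.1.1 plans "Subjects will be enrolled into a non-HIV+ cohort (n=12) to further expand pharmacokinetic investigations" and also "up to 28 HIV+ cervical cancer patients (including the patients who were treated at the RP2D during the dose escalation stage"). That is 12 + 28 = 40, or 12 + 28 + 6 = 46 in the 13.2.1 case where "none of the 6 patients on the MTD (or RP2D) is HIV+ cervical cancer patient". It could be more, because eligible treated patients replaced under 13.2.1 stay in the 13.3.1 set. A count of 23 in 40 or 46 would pass at 65% with probability 0.88 or 0.99, but 13.3.4 ties 23 to 28 patients and no section proposes that use.

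What remains is that the 28 are not identified. The number is the HIV+ cohort size in 5.4.1 and 13.1.1, and also the number of RP2D patients assumed for bioavailability in 13.1 and 13.3.5.

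**What to change.** 1. In 11.1.1 and 13.3.4, make the 13.3.1 efficacy set the denominator for mCR and ORR, at the RP2D and in each cohort. Keep the 11.1.1 evaluable population, including its non-target route, as a sensitivity analysis.
2. Count a patient without a 3-month PET, for whatever reason, as non-mCR. For ORR, count a patient without an adequate RECIST assessment as a non-responder. Do not tie ORR to the PET alone, since 11.1.3 notes that its CT part is not always adequate for RECIST.
3. In 13.3.4, state which 28 treated patients the 23/28 rule covers. Keep that denominator fixed, with no replacement for a missing PET, and say whether eligible treated patients replaced for DLT evaluability under 13.2.1 are among them. If another set or number is used, re-derive the count before the analysis.

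The cost is wording in 11.1.1 and 13.3.4 and one sponsor decision on the 28. No patients, scans or treatment changes are needed. The reported mCR and ORR may be slightly lower.

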#### 11.1.2 Disease Parameters

Measurable disease. Measurable lesions are defined as those that can be accurately measured in at least one dimension (longest diameter to be recorded) as  $\geq 20$  mm ( $\geq 2$  cm) by chest x-ray or as  $\geq 10$  mm ( $\geq 1$  cm) with CT scan, MRI, or calipers by clinical exam. All tumor measurements must be recorded in millimeters (or decimal fractions of centimeters).

Note: Tumor lesions that are situated in a previously irradiated area might or might not be

considered measurable. *If the investigator thinks it appropriate to include them, the conditions under which such lesions should be considered must be defined in the protocol.*

Malignant lymph nodes. To be considered pathologically enlarged and measurable, a lymph node must be  $\geq 15$  mm ( $\geq 1.5$  cm) in short axis when assessed by CT scan (CT scan slice thickness recommended to be no greater than 5 mm [0.5 cm]). At baseline and in follow-up, only the short axis will be measured and followed.

Non-measurable disease. All other lesions (or sites of disease), including small lesions (longest diameter  $< 10$  mm [ $< 1$  cm] or pathological lymph nodes with  $\geq 10$  to  $< 15$  mm [ $\geq 1$  to  $< 1.5$  cm] short axis), are considered non-measurable disease. Bone lesions, leptomeningeal disease, ascites, pleural/pericardial effusions, lymphangitis cutis/pulmonitis, inflammatory breast disease, and abdominal masses (not followed by CT or MRI), are considered as non-measurable.

Note: Cystic lesions that meet the criteria for radiographically defined simple cysts should not be considered as malignant lesions (neither measurable nor non-measurable) since they are, by definition, simple cysts.

‘Cystic lesions’ thought to represent cystic metastases can be considered as measurable lesions, if they meet the definition of measurability described above. However, if non-cystic lesions are present in the same patient, these are preferred for selection as target lesions.

Target lesions. All measurable lesions up to a maximum of 2 lesions per organ and 5 lesions in total, representative of all involved organs, should be identified as **target lesions** and recorded and measured at baseline. Target lesions should be selected on the basis of their size (lesions with the longest diameter), be representative of all involved organs, but in addition should be those that lend themselves to reproducible repeated measurements. It may be the case that, on occasion, the largest lesion does not lend itself to reproducible measurement in which circumstance the next largest lesion which can be measured reproducibly should be selected. A sum of the diameters (longest for non-nodal lesions, short axis for nodal lesions) for all target lesions will be calculated and reported as the baseline sum diameters. If lymph nodes are to be included in the sum, then only the short axis is added into the sum. The baseline sum diameters will be used as reference to further characterize any objective tumor regression in the measurable dimension of the disease.

Non-target lesions. All other lesions (or sites of disease) including any measurable lesions over and above the 5 target lesions should be identified as **non-target lesions** and should also be recorded at baseline. Measurements of these lesions are not required, but the presence, absence, or in rare cases unequivocal progression of each should be noted throughout follow-up.

#### 11.1.3 Methods for Evaluation of Measurable Disease

All measurements should be taken and recorded in metric notation using a ruler or calipers. All baseline evaluations should be performed as closely as possible to the beginning of treatment and never more than 4 weeks before the beginning of the treatment.

The same method of assessment and the same technique should be used to characterize each identified and reported lesion at baseline and during follow-up. Imaging-based evaluation is preferred to evaluation by clinical examination unless the lesion(s) being followed cannot be imaged but are assessable by clinical exam.

Clinical lesions Clinical lesions will only be considered measurable when they are superficial (e.g., skin nodules and palpable lymph nodes) and  $\geq 10$  mm ( $\geq 1$  cm) diameter as assessed using calipers (e.g., skin nodules). In the case of skin lesions, documentation by color photography, including a ruler to estimate the size of the lesion, is recommended.

Chest x-ray Lesions on chest x-ray are acceptable as measurable lesions when they are clearly defined and surrounded by aerated lung. However, CT is preferable.

Conventional CT and MRI This guideline has defined measurability of lesions on CT scan based on the assumption that CT slice thickness is 5 mm (0.5 cm) or less. If CT scans have slice thickness greater than 5 mm (0.5 cm), the minimum size for a measurable lesion should be twice the slice thickness. MRI is also acceptable in certain situations (e.g. for body scans).

Use of MRI remains a complex issue. MRI has excellent contrast, spatial, and temporal resolution; however, there are many image acquisition variables involved in MRI, which greatly impact image quality, lesion conspicuity, and measurement. Furthermore, the availability of MRI is variable globally. As with CT, if an MRI is performed, the technical specifications of the scanning sequences used should be optimized for the evaluation of the type and site of disease. Furthermore, as with CT, the modality used at follow-up should be the same as was used at baseline and the lesions should be measured/assessed on the same pulse sequence. It is beyond the scope of the RECIST guidelines to prescribe specific MRI pulse sequence parameters for all scanners, body parts, and diseases. Ideally, the same type of scanner should be used and the image acquisition protocol should be followed as closely as possible to prior scans. Body scans should be performed with breath-hold scanning techniques, if possible.

PET-CT At present, the low dose or attenuation correction CT portion of a combined PET-CT is not always of optimal diagnostic CT quality for use with RECIST measurements. However, if the site can document that the CT performed as part of a PET-CT is of identical diagnostic quality to a diagnostic CT (with IV and oral contrast), then the CT portion of the PET-CT can be used for RECIST measurements and can be used interchangeably with conventional CT in accurately measuring cancer lesions over time. Note, however, that the PET portion of the CT introduces additional data which may bias an investigator if it is not routinely or serially performed.

Ultrasound Ultrasound is not useful in assessment of lesion size and should not be used as a method of measurement. Ultrasound examinations cannot be reproduced in their entirety for independent review at a later date and, because they are operator dependent, it cannot be guaranteed that the same technique and measurements will be taken from one assessment to the next. If new lesions are identified by ultrasound in the course of the

study, confirmation by CT or MRI is advised. If there is concern about radiation exposure at CT, MRI may be used instead of CT in selected instances.

Endoscopy, Laparoscopy The utilization of these techniques for objective tumor evaluation is not advised. However, such techniques may be useful to confirm complete pathological response when biopsies are obtained or to determine relapse in trials where recurrence following complete response (CR) or surgical resection is an endpoint.

Tumor markers Tumor markers alone cannot be used to assess response. If markers are initially above the upper normal limit, they must normalize for a patient to be considered in complete clinical response. Specific guidelines for both CA-125 response (in recurrent ovarian cancer) and PSA response (in recurrent prostate cancer) have been published [JNCI 96:487-488, 2004; J Clin Oncol 17, 3461-3467, 1999; J Clin Oncol 26:1148-1159, 2008]. In addition, the Gynecologic Cancer Intergroup has developed CA-125 progression criteria which are to be integrated with objective tumor assessment for use in first-line trials in ovarian cancer [JNCI 92:1534-1535, 2000].

Cytology, Histology These techniques can be used to differentiate between partial responses (PR) and complete responses (CR) in rare cases (e.g., residual lesions in tumor types, such as germ cell tumors, where known residual benign tumors can remain).

The cytological confirmation of the neoplastic origin of any effusion that appears or worsens during treatment when the measurable tumor has met criteria for response or stable disease is mandatory to differentiate between response or stable disease (an effusion may be a side effect of the treatment) and progressive disease.

FDG-PET While FDG-PET response assessments need additional study, it is sometimes reasonable to incorporate the use of FDG-PET scanning to complement CT scanning in assessment of progression (particularly possible 'new' disease). New lesions on the basis of FDG-PET imaging can be identified according to the following algorithm:

- a. Negative FDG-PET at baseline, with a positive FDG-PET at follow-up is a sign of PD based on a new lesion.
- b. No FDG-PET at baseline and a positive FDG-PET at follow-up: If the positive FDG-PET at follow-up corresponds to a new site of disease confirmed by CT, this is PD. If the positive FDG-PET at follow-up is not confirmed as a new site of disease on CT, additional follow-up CT scans are needed to determine if there is truly progression occurring at that site (if so, the date of PD will be the date of the initial abnormal FDG-PET scan). If the positive FDG-PET at follow-up corresponds to a pre-existing site of disease on CT that is not progressing on the basis of the anatomic images, this is not PD.
- c. FDG-PET may be used to upgrade a response to a CR in a manner similar to a biopsy in cases where a residual radiographic abnormality is thought to represent fibrosis or scarring. The use of FDG-PET in this circumstance should be prospectively described in the protocol and supported by disease-specific medical literature for the indication. However, it must be acknowledged that both approaches may lead to false positive CR due to limitations of FDG-PET and biopsy resolution/sensitivity.

Note: A ‘positive’ FDG-PET scan lesion means one which is FDG avid with an uptake greater than twice that of the surrounding tissue on the attenuation corrected image.

